5.0 Procedures Involved

5.1 Study Design: aim #1 will be accomplished via a pre-post interventional design to evaluate changes in CT measurements of thumb radial subluxation (cm) from pre-intervention to intervention completion (9 weeks). The 9-week assessment will be the primary follow-up.

Aim #2 will be accomplished with a cross-sectional concurrent validity study design. Patients enrolled in the DS exercise intervention study will undergo additional assessment of metacarpal subluxation with ultrasound during baseline and week 9 evaluations.

5.2 Study Procedures:

Aim #1.

Screening and consenting: [name] has provided the CTSI's **BPIC** service with the diagnostic inclusion criteria for the study and will be informed within 3-5 days if a patient who meets these criteria is scheduled at the MHealth Clinics and Surgery Center. [name] will be present during the Study Orthopedist's clinic when these potentially eligible patients are scheduled for appointments. The study orthopedist will screen patients for pregnancy/risk of pregnancy via interview and present the study to the eligible patient and, if interested, the informed consent process will follow. [name] or other IRB-approved personnel will be responsible for informed consent. After consenting, baseline assessments will be conducted.

Assessment: CT will be used at prior to beginning aforementioned rehabilitation intervention, and after completing intervention (9 weeks) as per the European guidelines on quality criteria for computed tomography.³⁴ A validated positioning jig reproduced by our lab³⁵ will be used to maintain standardized joint positioning as the volunteer participates in dynamic pinch activities during CT examination. “Radial subluxation” (i.e., the displacement of thumb metacarpal base from the lateral border of the trapezium)³⁶ is a measure of thumb CMC instability and will be measured in centimeters. Subluxation measurements will not be made until after participants complete the 8-week protocol. After which, de-identified CT images will be presented to study orthopedic surgeon by the PI in a randomized sequence of baseline, and 9 week films so as to not introduce bias. Four images will be taken for each affected hand:

MEDICAL PROTOCOL (HRP-590)

PROTOCOL TITLE: Mechanisms of a Dynamic Stability Approach

VERSION DATE: 05/25/2023

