Assessment	Screening , Baseline: Visit 1 (Day 0, Week1)	Treatment Visit 1 (Week 1)	Treatment Visit 2 (Week 3)	Treatment Visit 3(Week 5)	Treatment Visit 4 (Week 7)	Follow-up #1 (Week 9)
Informed Consent Form	X					
Demographics	X					
Medical History/Arthritic staging	X					
Inclusion/Exclusion Criteria (Including radiographic confirmation of OA via fluoroscopy)	X					
Attestation of certainty of not being pregnant by women who are non-post menopausal	X					
Enrollment	X					
CT Measurements (Aim 1)	X					X

MEDICAL PROTOCOL (HRP-590)

PROTOCOL TITLE: Mechanisms of a Dynamic Stability Approach

VERSION DATE: 05/25/2023

Ultrasound measurements (Aim 2)	x					x
Self-reported disability (Michigan Hand Questionnaire) – Aim 1b	x					x
Treatment Adherence (Exercise Log) – Aim 1b		x	x	x	x	x
Adverse Events		x	x	x	x	x

Note: "Week" = 7 days +/-3 days

5.3 Study Duration:

- Duration anticipated for an individual participant's participation in the study: 9 weeks
- The duration anticipated to enroll all study participants: 3 years
- The duration anticipated to complete all study procedures: 4 years

5.4 Use of radiation:

Note: the following calculations are based on static radiographic imagining.

Radiation exposures (Aim#1) will be minimized through, short exposure times, and wear of leaded aprons, thyroid shields, and protective eyewear for the participant.

Leaded aprons, thyroid shields, and leaded eye protection will worn by the evaluators and participants throughout each CT assessment. Without the attenuation expected from the above protective measures, a conservative estimate of maximal radiation exposure per session is 0.0078 mSv (totaling 0.1248 mSv) when both thumbs are measured and 0.0624 mSv when only measuring one.

This exposure would respectively equate to 2.3% (unilateral) or 4.6% (bilateral) of the radiation one is naturally exposed to each year as a resident of Minnesota (3 mSv).⁴² Additionally, because investigators will not be working near but not within the beam of the CT device so there is no risk to the investigators.

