6.4 Sharing of genetic testing: N/A

7.0 **Sharing of Results with Participants.**

7.1 Sharing of results with participants: We plan to share a brief summary of aggregated study results with participants either by email or USPS delivery depending on the participant's preference and will include a "thank you" note for participating. We plan to use the CTSI Dissemination Toolkit when framing the language.

8.0 **Study Population**

8.1 Inclusion Criteria: will include:

- Adults 18 years or older
- having radiographically-confirmed thumb CMC OA
- having been referred to occupational therapy.

A study orthopedist will use current radiographic evidence to screen and stage thumb CMC OA in all prospective candidates to ensure the diagnostic criteria required for inclusion are met. The same study orthopedist will screen recruits for pregnancy or risk of pregnancy via an interview. Both men and women will be included given the findings of Wilder et al.²⁹, who described the prevalence of radiographically confirmed thumb carpometacarpal osteoarthritis to be similar in men (20%) and women (21%).

In addition, should these recruitment efforts prove to be slow we will recruit through the existing health records of adults ages 18 and older who have a diagnosis of CMC OA and have received care within University of Minnesota Health/Fairview orthopedics/ Sports Medicine, or Rheumatology departments from December 2015 to April 30, 2023 Eligible participants will have any of the following ICD 10 codes: Primary OA CMC joint (M18.11, M18.12, M18.2), post-traumatic OA CMC joint (M18.31, M18.32, M18.4) and other secondary OA CMC joint (M18.51, M18.52) and will be identified via the I2B2 Data set and then run by BPIC and sent to Fairview for mailing. Alternatively, Fairview's Research Recruitment services may perform the same service.

Those recruited in this fashion will be required to be screened for pregnancy or risk of pregnancy via an interview by their preferred medical provider (i.e., women's health, family physician, internal medicine, orthopedic surgeon) prior to enrollment.

8.2 Exclusion Criteria will include:

- cortisone treatments to the affected thumb within the prior three months
- thumb CMC joint replacement
- a diagnosis of inflammatory arthritis
- a diagnosis of Ehlers Danlos Syndrome
- a diagnosis of Marfan's disease
- pregnancy or questionable pregnancy
- mothers who are breastfeeding

MEDICAL PROTOCOL (HRP-590)

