PROTOCOL TITLE: Mechanisms of a Dynamic Stability Approach

VERSION DATE: 05/25/2023

- cognitive disorders which would preclude a client from following the testing commands and home program participation
- a diagnosis of a concomitant condition affecting the arthritic thumb (i.e. Wartenberg's syndrome, deQuervain's, trigger thumb, intersection syndrome)
- grade 4 Eaton²⁹ OA staging
- ongoing hand rehabilitation (i.e., within prior 6 months)
- pain which precludes participants from completing testing
- an EMR flag for not wishing to participate in research

8.3 Screening: [name] has provided the CTSI's BPIC service with the diagnostic inclusion criteria for the study and will be informed within 3-5 days if a patient who meets these criteria is scheduled at the MHealth Clinics and Surgery Center. [name] will be present during the Study Orthopedist's clinic when these potentially eligible patients are scheduled for appointments. A study orthopedist will use current radiographic evidence to screen and stage thumb CMC OA in all prospective candidates to ensure the diagnostic criteria required for inclusion are met. The same study orthopedist will screen recruits for pregnancy or risk of pregnancy via an interview and present the study to the eligible patient. If the recruit is interested, the informed consent process will follow and will be conducted by [name] or other IRB-approved personnel.

9.0 Vulnerable Populations:

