12.0 Withdrawal of Participants

MEDICAL PROTOCOL (HRP-590)

PROTOCOL TITLE: Mechanisms of a Dynamic Stability Approach

VERSION DATE: 05/25/2023

12.1 Withdrawal Circumstances:

An investigator may discontinue a participant from the study for the following reasons:

- Significant study intervention non-compliance
- If any clinical adverse event (AE), laboratory abnormality, or other medical condition or situation occurs such that continued participation in the study would not be in the best interest of the participant
- If the participant meets an exclusion criterion (either newly developed or not previously recognized) that precludes further study participation
- If they are lost to follow up
- If they behave inappropriately toward study staff
- Disease progression which requires discontinuation of the study intervention
- If they show signs of diminished capacity to consent
- Or it is in their best interest, as determined by the PI

Recruits will be informed that participation in this study is voluntary. They will be informed that their decision on whether or not to participate in this study will not affect their current or future relations with the University, University of Minnesota Medical Center, or Fairview. Recruits will be informed that, if they decide to participate, they are free to withdraw at any time without affecting those relationships.

12.2 Withdrawal Procedures: If participants choose to withdraw from the study, data collection will be discontinued with no further follow up. Participants who are withdrawing from the study will be asked to consider providing consent for subsequent data collection to follow up on their medical outcomes related to the project. Thus, participants will be presented with the option to sign a "Consent Collection after Withdrawal" to enable this future data collection. All data collected up to the point of participant withdrawal from the study will continue to be securely stored and analyzed. Primary and secondary outcomes will be handled through intent to treat analysis. Records will be kept on number of withdrawals as well as the reasoning for such.

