13.2 Reproduction Risks: Use of radiographic imaging is contraindicated for pregnant women. As such, women who are or could be pregnant will be excluded from this study.

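### Minor safety gap: the pregnancy attestation is scheduled at baseline only, although the research CT is repeated at week 9

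*Combined protocol and SAP*

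**What the plan says.** **Rule.** Section 13.2 states "Use of radiographic imaging is contraindicated for pregnant women" and adds that "women who are or could be pregnant will be excluded from this study". Section 8.2 lists "pregnancy or questionable pregnancy" among the exclusions. Section 9.3 gives ionizing radiation as the reason.

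**Checks.** All those described are at or before enrolment:
- Section 5.2, clinic route: "The study orthopedist will screen patients for pregnancy/risk of pregnancy via interview". This comes before consent.
- Sections 8.1 and 8.3 repeat it: "The same study orthopedist will screen recruits for pregnancy or risk of pregnancy via an interview".
- Section 8.1, health-record route: recruits are "screened for pregnancy or risk of pregnancy via an interview by their preferred medical provider" before enrolment.
- Section 5.2, schedule: the row "Attestation of certainty of not being pregnant by women who are non-post menopausal" is marked in the screening and baseline column only.

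**Exposures.** The same schedule marks CT at baseline and at Follow-up #1 (Week 9). Section 5.2 gives four images per affected hand per visit, so 8 acquisitions over the study for one thumb and 16 for two. It also classes the CT as additional to standard care.

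**Nearest safeguard.** Section 12.1 lets the investigator discontinue a participant on this ground: "If the participant meets an exclusion criterion (either newly developed or not previously recognized) that precludes further study participation".

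**Dose statement.** Section 5.4 gives 0.0078 mSv per session, totals of 0.0624 mSv (one thumb) and 0.1248 mSv (two), and shares of 2.3% and 4.6% of a 3 mSv annual background.

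**The concern.** The exclusion exists because of the radiation, so it should hold at each research exposure. As written, it is applied before the first of two scans and not before the second. A woman who becomes pregnant during the intervention could reach the week-9 CT without any scheduled step that asks her. Followed to the letter, the plan then allows an exposure that its own section 13.2 calls contraindicated. No endpoint or analysis is affected; what is at stake is whether a stated participant protection is carried through.

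**Working it through.** **1. Schedule, side by side (section 5.2).**

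| Row | Baseline | Week 9 |
|---|---|---|
| Pregnancy attestation | marked | not marked |
| CT | marked | marked |

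Section 12.1 permits discontinuation for a newly developed exclusion criterion but schedules nothing to detect one. Section 18.2 has the principal investigator ask about adverse events at each contact, but does not describe asking about pregnancy.

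**2. Age of the attestation at the second CT.** Baseline is day 0 in week 1, and the schedule allows +/-3 days. Counting from week 1 to week 9 gives 8 x 7 = 56 days; counting nine full weeks gives 9 x 7 = 63 days. With the window: 56 - 3 = 53 to 63 + 3 = 66 days.

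**3. Dose, reproducing the plan's totals first (section 5.4 dose, section 5.2 counts).**
- One thumb: 0.0078 x 8 = 0.0624 mSv. Matches.
- Two thumbs: 0.0078 x 16 = 0.1248 mSv. Matches.

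The totals work only if 0.0078 mSv is the dose of one acquisition. As a dose per visit it would total 2 x 0.0078 = 0.0156 mSv. Section 3.1 uses the word session for the CT visit, so the label in 5.4 is a slip.

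**4. Dose at the second CT.** It is half of the acquisitions:
- One thumb: 4 x 0.0078 = 0.0312 mSv
- Two thumbs: 8 x 0.0078 = 0.0624 mSv

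Background per day is 3/365 = 0.00822 mSv, so these are 0.0312/0.00822 = 3.8 days and 0.0624/0.00822 = 7.6 days of background.

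**5. Background shares.**
- One thumb: 0.0624/3 = 2.08%, stated as 2.3%
- Two thumbs: 0.1248/3 = 4.16%, stated as 4.6%

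The stated shares are too high by a factor of 2.3/2.08 = 4.6/4.16 = 1.106. They would need a background of 0.0624/0.023 = 2.71 mSv rather than 3.

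**6. How many women would be asked.** The section 11.1 pool is 3363/4858 = 69.2% women. Section 10.1 allows 40 to 50 participants, so 40 x 0.692 = 27.7 to 50 x 0.692 = 34.6 women if enrolment mirrors the pool. The documents do not give the share who are not post-menopausal. Assuming 5% to 20%: 27.7 x 0.05 = 1.4 to 34.6 x 0.20 = 6.9, so about 1 to 7 women. This counts women asked, not pregnancies.

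**The case against.** The case for leaving the plan alone has several parts.

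- **Harm is very small.** The hand is imaged, lead aprons are worn, and the second scan equals about 4 to 8 days of background. Section 9.3 expects the exclusion to touch very few recruits. This stands, and it is why the point is minor.
- **The entry screen is broad.** It covers risk of pregnancy and questionable pregnancy, which could be read as looking ahead. That narrows the group but does not close the gap: women who are not post-menopausal can still enrol on the attestation, and adults from 18 are eligible.
- **Partial safeguards exist.** There are four treatment visits before week 9, adverse-event questioning, and the discretionary rule in 12.1. None is a scheduled pregnancy check.
- **A check may exist elsewhere.** The ancillary review table requires radiation committee (AURPC) approval before IRB approval. That application, the consent pages and the imaging centre's procedures are not visible. This limits the claim to the protocol text.
- **The 5.4 slips are harmless.** The totals are right, and the wrong percentages overstate exposure. Agreed; they are editorial.

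A reader might also infer that the true dose exceeds the stated one, because 5.4 bases its figures on static radiographic imaging while the study uses 3-second CT acquisitions. The documents do not support that. Section 5.4 discloses its basis, nothing in the protocol shows the figure to be wrong, and no error can be calculated from it.

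**Conclusion.** The gap holds as a minor safety point. The protocol's pregnancy rule is checked before the first research CT, and no visible section schedules a check before the second, 53 to 66 days later. The exposure concerned is 0.0312 to 0.0624 mSv on the protocol's own figure, and few cases, if any, are expected. The estimate of 1 to 7 women asked rests on an assumed 5% to 20% who are not post-menopausal and on enrolment mirroring the recruitment pool.

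Two stronger readings should be resisted. The documents do not show that the dose is more than minimal or that participants face material harm. Nor do they show that no check will happen in practice, since the imaging centre may ask as routine.

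The two corrections in 5.4 are certain as arithmetic and change no conclusion.

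**What to change.** **Schedule (5.2).** Mark the attestation row at Follow-up #1 (Week 9), to be completed before CT by women who are not post-menopausal.

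**Section 13.2.** State that the week-9 CT is omitted if the answer is pregnant or unsure, and that the questionnaire is still completed. Ultrasound may be done if wanted, but would have no CT comparator at that visit; section 15.1 in any case specifies the agreement analysis on baseline measurements.

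**Section 5.4, editorial.** Call 0.0078 mSv a dose per acquisition, give 0.0312 mSv (one thumb) and 0.0624 mSv (two) per CT visit beside the existing totals, and correct the shares to 2.1% and 4.2%.

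**Cost.** One question for a handful of women, and wording edits. A woman whose scan is omitted would lack the primary outcome. Section 15.2 enrols 49 against 39 required, but the difference of 10 is the ordinary 20% loss-to-follow-up allowance (39/0.8 = 48.75, rounded up to 49), not spare capacity. Section 10.1 permits as few as 40 participants, which leaves 40 - 39 = 1. Any omitted scan would count against that margin, though few, if any, are expected.

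If the imaging centre or the radiation committee application already requires a check before each scan, a cross-reference in 13.2 is enough.

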unloaded lateral pinch, loaded lateral pinch, unloaded 3-point pinch, and loaded 3-point pinch. When unilateral thumb OA is present, eight 3-second CT assessments (unloaded lateral pinch x2, loaded lateral pinch x 2, unloaded 3 point pinch x 2, and loaded 3-point pinch x2) will occur by the time of the 9 week follow-up. In the instance that the participant has bilateral CMC OA, 16 three-second assessments will occur. If participants have not yet had an x-ray confirmation of arthritis, through fluoroscopy will be billed to participant's insurance but CT assessments will all be billed to research.

Computerized tomography data will be recorded through use of the Siemens Biograph MCT 64 slice PET/CT at U of MN's Center for Clinical Imaging Research (CCIR). CT images will be used to capture 'kinematic' data and a wireless biometrics digital pinch meter will be used to capture the pinch 'kinetic' data.

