13.0 Risks to Participants

13.1 Foreseeable Risks: This proposed study involves human subjects. Human subjects are required for this study as we plan to test the effects of an intervention on human adults with thumb arthritis. This study cannot be carried out in an animal model nor does it pose any significant risks to the health and wellbeing of human subjects. 1) Participants might experience some mild hand fatigue or joint aches for 2-3 days following testing and at the onset of the intervention as a result of the repetitive nature of the tasks involved, 2) participants will be asked to give some information that you may be perceived to be of a personal nature 3) the primary outcome measure for this study is CT and this involves the aforementioned minimal amounts of ionizing radiation, and 4) at times, it may be necessary for the researchers to physically touch the participants' hands or sides to ensure that you are in the correct positions. This, to some, may be uncomfortable.

Radiation exposures will be minimized through short exposure times, and wear of leaded aprons, thyroid shields, and protective eyewear for the participant and rater alike, and leaded gloves for the rater.³⁹⁻⁴¹

Participants will be allowed frequent rest breaks to limit any amount of fatigue and soreness participants may experience in their hands and arms following testing and when participating in exercise. If discomfort increases as a result of testing, participants will be instructed on self-managing symptoms through use of physical agents such as cryotherapy and rest. In the event that this research activity results in an injury, treatment will be available, including first aid, emergency treatment and follow-up care as needed. Participants who believe they have suffered a research related injury, will be asked to inform the researchers immediately. If participants are physically uncomfortable or uncomfortable with the nature of the questions or occasional touch, they will be instructed that they are free to withdraw from participation at any time without any impact to relationships with the university.

Privacy/Confidentiality Risks: Risk of loss of confidentiality is unlikely, but could possibly occur as PHI is utilized as part of this study. This risk would be minimized by protections such as de-identification of participants via use of a study identifier, locked/secured/limited access to PHI, and electronic data securely stored and password-protected.

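### The radiation estimate in Section 5.4 rests on static radiographic imaging and is not shown to be conservative or maximal for the three-second CT acquisitions in Section 5.2

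*Combined protocol and SAP*

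**What the plan says.** Section 5.4 (Use of radiation) states its basis first: "Note: the following calculations are based on static radiographic imagining". Setting aside any attenuation from shielding, it then gives "a conservative estimate of maximal radiation exposure per session is 0.0078 mSv (totaling 0.1248 mSv) when both thumbs are measured". For a single thumb, the total it states is "0.0624 mSv when only measuring one". It compares these with an annual background of 3 mSv: "This exposure would respectively equate to 2.3% (unilateral) or 4.6% (bilateral) of the radiation one is naturally exposed to each year".

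Section 5.2 (Study Procedures, Assessment) describes the imaging. A jig standardises the joint position "as the volunteer participates in dynamic pinch activities during CT examination". Each affected hand has four images per visit: lateral and 3-point pinch, each unloaded and loaded. Over the two visits this makes "eight 3-second CT assessments" for unilateral disease and 16 for bilateral disease. The scanner is a 64-slice PET/CT, and the images are meant to supply kinematic data.

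Section 13.1 (Foreseeable Risks) refers back to the Section 5.4 estimate without its caveat: "the primary outcome measure for this study is CT and this involves the aforementioned minimal amounts of ionizing radiation".

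**The concern.** The stated basis of the estimate and the described procedure do not match. One is static radiographic imaging. The other is a three-second CT acquisition while the participant pinches. Nothing in the documents connects the two. They give no CT dose index, dose-length product, scan length, tube settings or effective dose for one acquisition, and no argument that the static figure is an upper bound. Without that link, calling the result conservative and maximal is an assertion.

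At stake is safety information, not an endpoint, the power or an analysis. Section 5.2 says that the CT measurements go beyond standard care, so their radiation is a risk taken only for research. Section 13.1 describes that risk by pointing to the Section 5.4 figure.

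**Working it through.** **Inputs.** From Section 5.4: unit dose 0.0078 mSv; totals 0.0624 mSv (one thumb) and 0.1248 mSv (both); shares 2.3% and 4.6%; background 3 mSv per year. From Section 5.2: 8 acquisitions (unilateral) or 16 (bilateral) over two imaging visits.

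**Step 1: reproduce the totals.** Total = unit dose × number of acquisitions.
- One thumb: 0.0078 × 8 = 0.0624 mSv.
- Both thumbs: 0.0078 × 16 = 0.1248 mSv.

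Both match exactly, so the planned acquisitions are fully counted.

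**Step 2: check the unit label.** Section 5.4 attaches 0.0078 mSv to a session. With two imaging sessions that would give 0.0078 × 2 = 0.0156 mSv, which is neither printed total. The totals reproduce only if 0.0078 mSv is the dose of one acquisition. A session would then be 0.0078 × 4 = 0.0312 mSv for one thumb and 0.0078 × 8 = 0.0624 mSv for both.

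**Step 3: check the shares of background.**
- 0.0624 / 3 = 2.08%; printed 2.3%.
- 0.1248 / 3 = 4.16%; printed 4.6%.

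The printed shares would need a background of 0.0624 / 0.023 = 2.71 mSv, or totals of 0.023 × 3 = 0.069 mSv and 0.046 × 3 = 0.138 mSv. Section 5.4 gives none of these. The printed shares are slightly higher than the totals support, so this slip does not flatter the study.

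**Step 4: see what depends on the unit dose.** Let d be the effective dose of one three-second CT acquisition. The totals are 8d and 16d. The documents do not give d, so the corrected total cannot be computed. The claim of a maximum holds only if d is at most 0.0078 mSv. The ratios below are assumed, only to show how the totals scale. None comes from the documents.

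| Assumed d / 0.0078 | One thumb, mSv (share of 3 mSv) | Both thumbs, mSv (share of 3 mSv) |
|---|---|---|
| 0.5 | 0.0312 (1.04%) | 0.0624 (2.08%) |
| 1 | 0.0624 (2.08%) | 0.1248 (4.16%) |
| 2 | 0.1248 (4.16%) | 0.2496 (8.32%) |
| 5 | 0.312 (10.4%) | 0.624 (20.8%) |
| 10 | 0.624 (20.8%) | 1.248 (41.6%) |

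Any error in the unit dose passes to the total in full proportion.

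**The case against.** The strongest reply is that the protocol uses radiographic loosely. Aim 1 in Section 1.1 speaks of radiographic misalignment measured by CT, and Section 13.2 uses the word where the study imaging is CT. The note in Section 5.4 may therefore mean static CT. Section 5.2 also speaks of images taken in a jig that holds position, so the contrast between static and dynamic is not clean. This stands to the extent that a reader might infer the figure is a plain-film dose, and the documents do not establish that. The gap remains on either reading, because no dose for a three-second CT acquisition is given.

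A second reply is that the estimate is conservative because it ignores shielding. That makes it conservative with respect to shielding only. It says nothing on whether the unit dose suits the acquisition performed.

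A third is that the note discloses the basis. It does, but the same section then calls the result a maximum, and Section 13.1 repeats it without the caveat.

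A reader might also infer that the radiation text was left over from a fluoroscopy design, since Section 13.1 mentions leaded gloves for the rater and cites fluoroscopy studies (references 39–41). The evidence is circumstantial. Those references support protective measures, not the dose, and fluoroscopy remains in the current protocol as the baseline diagnostic assessment.

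Finally, a reader might infer that the radiation committee or participants were given a wrong figure. That cannot be known. The ancillary review table calls for a separate radiation application whose content is not in these documents, and the consent pages are not available for review.

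**Conclusion.** The point holds as one of unsupported and inconsistent safety information. Section 5.4 does not show that 0.0078 mSv, or the totals built on it, is conservative or maximal for the CT procedure in Section 5.2, and Section 13.1 relies on it. This rests on the protocol's own description of its basis and on the absence of any CT dose input. It does not depend on which sense of radiographic was intended.

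The size of any error cannot be stated. A tempting stronger reading is that exposure is understated by some multiple. The documents support neither a multiple nor a direction, and the true exposure may be small. Nor were acquisitions left out: 8 and 16 are already in the totals.

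Two smaller faults are certain from arithmetic alone: the per-session label, and the percentages, which should read 2.08% and 4.16% if the totals and the 3 mSv background stand. The correction should be made, but the documents demonstrate no harm and no effect on the trial's inference.

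**What to change.** Reconcile Sections 5.2, 5.4 and 13.1:

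- Recalculate the exposure in Section 5.4 from the CT acquisition protocol on the named scanner: estimated dose of one three-second acquisition, times 8 for one thumb or 16 for both. State the source of the unit dose.
- Label the unit dose per acquisition, and recompute the shares of background from the new totals.
- Remove the words conservative and maximal unless the CT figure supports them.
- Carry the result into Section 13.1, and into any radiation application or participant information that uses the present figure.

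The cost is one dose calculation and wording edits. If a CT estimate already exists in the radiation application, the work is to copy it across. The downside is that the stated exposure may become less favourable. No change to the imaging itself is proposed.
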